4.4.2.2.5 Duration

Duration is derived from the start and stop dates of the unsolicited non-serious AE provided in the clinical database:

- stop date of unsolicited non-serious AE - start date of unsolicited non-serious AE + 1.

The duration should be considered as missing only if one or both of the start and stop dates of the unsolicited non-serious AE is missing or partially missing.

4.4.2.3 SAEs

4.4.2.3.1 Last Vaccination

Last vaccination before any SAE is the study vaccination at V01.

4.4.2.3.2 Time of Onset

Time of onset will be computed using the same methodology as for unsolicited non-serious AEs described in [Section 4.4.2.2.4](#).

SAEs will be analyzed throughout the study using the following periods:

- During the study (i.e., all SAEs occurred during the study)
- Within 30 days after vaccination

An SAE with missing time of onset will be considered to have occurred just after the vaccination indicated by the visit number, so will be included in these tables.

Note: SAEs that occurred before vaccination (negative time of onset) will not be included in analysis, but will be listed separately.

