4.4.2.2.4 Time of Onset

Time of onset is derived from the start date of the unsolicited non-serious AE provided in the clinical database and the date of last vaccination:

- start date of the unsolicited non-serious AE – date of previous vaccination

The time of onset should be considered as missing only if one or both of the dates are missing or partially missing.

The unsolicited non-serious AEs will be analyzed "Within 30 days", which corresponds to AEs with a time of onset between 0 and 30 days after vaccination or missing. An AE with missing time

of onset will be considered to have occurred just after the vaccination indicated by the visit number, so will be included in these tables.

Note: Unsolicited non-serious AEs that occurred before vaccination (negative time of onset) or with a time of onset higher than defined above will not be included in analysis, but will be listed separately.

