5.3.1.5 Start Date and Stop Date

Missing or partially missing start dates for unsolicited AEs will remain missing and not be imputed. If either the start or stop date is missing or partially missing, the time of onset will be considered to be missing. Nevertheless unsolicited AEs with missing time of onset will be included in analyses according to the visit collected.

Missing or partially missing stop dates for AEs (solicited reactions and unsolicited AEs) will remain missing and not be imputed.

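### An SAE with only a partial start date is counted in the 30-day SAE table even when its recorded month and year rule out D0 to D30

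*SAP*

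**What the plan says.** Four SAP rules combine.

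- **Method (4.4.2.3.2).** For SAEs, "Time of onset will be computed using the same methodology as for unsolicited non-serious AEs described in" Section 4.4.2.2.4.
- **When onset is missing (4.4.2.2.4).** "The time of onset should be considered as missing only if one or both of the dates are missing or partially missing". The two dates are the event start and the previous vaccination.
- **Which vaccination (4.4.2.3.1).** "Last vaccination before any SAE is the study vaccination at V01".
- **What happens next (4.4.2.3.2).** "An SAE with missing time of onset will be considered to have occurred just after the vaccination indicated by the visit number", and the event goes into the SAE tables. Two periods are tabulated: the whole study, and "Within 30 days after vaccination".

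SAP 5.3.1.5 adds: "Missing or partially missing start dates for unsolicited AEs will remain missing and not be imputed". Neither document compares the known part of a date with the 30-day limit.

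**The concern.** Treating an event of unknown date as early is a familiar conservative convention. For non-serious AEs it does little harm: collection stops at Visit 2, between D30 and D44, so an event can be placed in the window when it began at most 14 days after it closed. SAEs are collected to D180 (+14 days), so the same convention can pull in an event that began 150 to 164 days after the window closed (180 − 30 and 194 − 30).

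The difficulty is confined to partial dates. When nothing is known about the date, an assumption is needed. When the month and year are known and exclude D0 to D30, the rule discards recorded information and assigns a window that the data contradict. A reader looks at the 30-day table for a temporal link between vaccination and serious events. Early SAEs may be few, so a single misplaced event could be visible there.

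**Working it through.** The documents give no figure on this point to reproduce. The check has two parts: following the rule on dates that the trial calendar allows, and illustrating the size under stated assumptions.

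**1. Following the rule.** Protocol 5.1.5 plans inclusion from 15 July 2016 to 04 November 2016. The earliest onset consistent with a month-and-year date is the first day of that month.

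| Vaccinated | SAE start recorded as | Earliest possible onset | Place under the written rule |
|---|---|---|---|
| 15 July 2016 | December 2016 | 1 December 2016 = D139 | both tables, including 30-day |
| 04 November 2016 | March 2017 | 1 March 2017 = D117 | both tables, including 30-day |

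In each case the start date is partial, so onset is missing. The event is then tied to D0 and tabulated in the 30-day window, although the record excludes it.

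**2. Direction.** A true early SAE with a partial date stays in the 30-day table. A late one is added to it. Nothing is removed, so the 30-day count can only rise. The during-study table includes the event either way.

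**3. Size.** Assumptions:
- SAE onset has a constant hazard over D0 to D, with D = 180 or 194.
- A share f of SAEs, early or late, lacks a full start date.

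The true share of SAEs starting in D0 to D30 is w = 31/(D + 1):
- D = 180: w = 31/181 = 17.1%, so 82.9% start later.
- D = 194: w = 31/195 = 15.9%, so 84.1% start later.

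The ratio of the tabulated to the true 30-day count is [w + (1 − w)f]/w = 1 + f(1 − w)/w. For D = 180 this is 1 + f × 150/31. For D = 194 it is 1 + f × 164/31.

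| f | D = 180 | D = 194 |
|---|---|---|
| 0% | 1.00 | 1.00 |
| 1% | 1.05 | 1.05 |
| 2% | 1.10 | 1.11 |
| 5% | 1.24 | 1.26 |
| 10% | 1.48 | 1.53 |

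To put this in counts, take 450 subjects per group (Protocol synopsis) and assume that 3% have an SAE, which gives 13.5 subjects. With D = 180 the true 30-day count is 13.5 × 0.171 = 2.3 (0.51%). It becomes 2.5 (0.56%) at f = 2%, 2.9 (0.64%) at f = 5% and 3.4 (0.76%) at f = 10%.

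These ratios count every late SAE without a full start date, including those whose date is wholly missing or does not settle the window. They are therefore an upper bound on what the proposed fix removes.

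**The case against.** The strongest reply is that partial SAE dates will be rare and the consequence slight. Much of this stands.

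- **Rarity.** Subjects are asked to notify the site at once of potential SAEs (Protocol 5.1.3). SAEs are reported within 24 hours on a physician-signed form (10.1), and the investigator must request medical records (10). Queries must be completed before database lock (11.2, 13.4.1), and a statistical data review is planned (SAP 5.6). A reader might infer that month-only dates are likely because some SAEs surface only at the 6-month call. The documents give no frequency, and these safeguards point the other way.
- **Consequence.** Safety is descriptive, with no hypothesis tested. The rule is the same in both groups of a blinded trial, and it errs towards over-reporting early harm. A reader might infer a biased comparison between vaccines, but nothing in the rule implies one.
- **A large relative increase.** A reader might picture one misplaced event added to two true early ones, a rise of 50%. Both counts would be invented. Under constant hazard, a rise of that order needs about 10% of SAEs to lack a full start date.
- **Early and related.** SAP 5.3.1.2 counts missing causality as related, so a reader might infer that a late event would appear as early and related. That also requires causality to be missing, whereas the investigator and then the sponsor's safety officer assess it for each SAE (Protocol 10.4).

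One reply does not stand. SAP 5.3.1.5 includes unsolicited AEs with missing onset by the visit at which they were collected, and 4.4.2.3.2 mentions the visit number. This might be meant to keep late-collected events out of the early table. But the SAE-specific sentence ties the visit number to a vaccination, there is only one, and no SAE period after day 30 is defined to receive such an event.

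A separate matter is that SAP 5.3.1.5 also says "If either the start or stop date is missing or partially missing, the time of onset will be considered to be missing". Taken literally, that would widen the problem to SAEs with a complete start date but no full stop date. It conflicts with 4.4.2.2.4, which derives onset from the start and vaccination dates. The two need reconciling, but the present point does not rest on it.

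**Conclusion.** The point holds as a minor correction. As written, the SAP places an SAE in the 30-day table even when its recorded month and year show that it began later. The mechanism and the upward direction follow from the text alone.

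The size cannot be determined from the documents. The multiples of about 1.05 to 1.48 (D0 to D180) rest on a constant hazard and an assumed 1% to 10% of SAEs without a full start date. If every SAE has a full start date, there is no effect. The during-study SAE count and the primary immunogenicity analysis are unaffected, and the between-group safety comparison need not be biased.

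**What to change.** Add to SAP 4.4.2.3.2: *An SAE with a partial start date is excluded from the 30-day table when the earliest start date consistent with the recorded month and year is later than D30; it is then counted only in the during-study table. An SAE with a wholly missing start date, or with a partial date that does not exclude D0 to D30, follows the current convention.*

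The contact at which an SAE was reported should not serve as evidence of late onset. The 6-month call asks about any unreported SAE since vaccination (Protocol 5.1.4), so an event first reported there may have begun early.

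The cost is one SAP passage and one date comparison in the derivation program. No new data are needed, and the conservative handling of unknown dates is kept.

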4.4.2.3.3 Duration

Duration will be computed using the same methodology as for unsolicited non-serious AEs described in [Section 4.4.2.2.5](#).

4.4.2.4 Medically-Attended Adverse Events (MAAEs)

MAAEs that occur from Visit 1 (D0) to Visit 2 (D30[+14days]) will be recorded as unsolicited AEs on the diary card as part of all unsolicited AEs collected for this post-vaccination period. Unsolicited AEs that have action taken categories 2 or 3 will be summarized and presented as MAAEs between Visit 1 and Visit 2. After that MAAEs will be collected from Visit 2 to 6

months, as applicable. Calculation methods are the same as unsolicited non-serious AEs as described in [Section 4.4.2.2](#).

4.4.2.5 Other Safety Endpoints

4.4.2.5.1 Pregnancy

This information will be listed as collected. No derivation or imputation will be done.

4.4.2.5.2 Action Taken

This information will be summarized as collected, including missing observations. No derivation or imputation will be done.

4.4.2.5.3 Seriousness

This information will be summarized as collected. No derivation or imputation will be done.

4.4.2.5.4 Outcome

This information will be summarized as collected. No derivation or imputation will be done.

4.4.2.5.5 Causality

This information will be summarized as collected. Missing causality (relationship) will be handled as described in [Section 5.3.1.2](#).

4.4.2.5.6 AEs Leading to Study Discontinuation

A flag is available in the clinical database for all AEs in order to identify AEs leading to discontinuation.

In general, the items that are counted are:

- Disposition table: A subject who has, on the termination form, the reason for early termination “Serious Adverse Event” or “Other adverse event” is checked.
- Safety overview table: A subject who has either the reason for early termination “Serious Adverse Event” or “Other adverse event” checked or lists an AE on an AE page (solicited, unsolicited, or SAE) that has “Reaction Leading to Termination” or “Event Leading to Termination” or “Serious Adverse Event Leading to Termination” checked on the termination form, that is at least Grade 1 and is within the time period indicated
- SOC/PT table: An event (solicited, unsolicited, or SAE) that has “Reaction Leading to Termination” or “Event Leading to Termination” or “Serious Adverse Event Leading to Termination” checked that is at least Grade 1 and is within the time period indicated

4.4.3 Efficacy

Not applicable

4.4.4 Derived Other Variables

4.4.4.1 Age for Demographics

Age in years: (Date of vaccination - Date of birth +1) / 365.25

4.4.4.2 Subject Duration

The duration of a subject in the study is computed as follows: Maximum (date of last visit, date of term form) – (date of Visit 1) +1.

The duration of a subject in the study including follow-up is computed as follows: Maximum (date of last visit, date of term form, last date of follow-up contact) – (date of Visit 1) +1.

4.4.4.3 Duration of the Study

The duration of the study (until last visit) is computed as follows: Maximum of all subjects (date of last visit, date of termination form) – minimum for all subjects (date of Visit 1) +1.

The duration of the study (including follow-up) is computed as follows: Maximum of all subjects (date of last visit, date of termination form, date of last follow-up contact) – minimum for all subjects (date of visit V01) +1

4.4.4.4 MAAEs from Visit 1 to Visit 2

MAAEs that occur from Visit 1 (D0) to Visit 2 (D30[+14days]) will be recorded as unsolicited AEs on the diary card as part of all unsolicited AEs collected for this post-vaccination period. The unsolicited AEs that have outcome categories 2 (health care provider contact) or 3 (Health care contact + Medication) will be summarized and presented as MAAEs during Visit 1 and Visit 2.

5 Statistical Methods and Determination of Sample Size

The statistical analyses will be performed under the responsibility of the Sponsor's Biostatistics platform using SAS[®] Version 9.4 software or later. The results of the statistical analysis will be available in the final clinical study report (CSR).

For descriptive purposes, the following statistics in [Table 5.1](#) will be presented. The confidence interval (CI) for the single proportion will be calculated using the exact binomial method (Clopper-Pearson method, quoted by Newcombe (6)). For immunogenicity results, assuming that Log₁₀ transformation of the titers / data follows a normal distribution, at first, the mean and the 95% CI will be calculated on Log₁₀ (titers / data) using the usual calculation for normal distribution (using Student's t distribution with n-1 degree of freedom), then antilog

transformations will be applied to the results of calculations, in order to provide geometric means (GMs) and their 95% CI.

Table 5.1: Descriptive statistics produced

Baseline characteristics and follow-up description	Categorical data	Number of subjects. Percentage of subjects.
	Continuous data	Mean, standard deviation, quartiles, minimum, and maximum.
Clinical safety results	Categorical data	Solicited: Number and percentage (95% CIs) of subjects. Unsolicited: Number and percentage (95% CIs) of subjects, and number of events.
Immunogenicity results	Categorical data (seroresponse, vaccine response, seroconversion, cutoff)	Number and percentage (95% CIs) of subjects.
	Continuous data (titer / data)	Log ₁₀ : Mean and standard deviation. Anti-Log ₁₀ (work on Log ₁₀ distribution, and anti-Log ₁₀ applied): Geometric mean (GM), 95% CI of the GM Graphical representation by Reverse Cumulative Distribution Curve (RCDC).

5.1 Statistical Methods

5.1.1 Hypotheses and Statistical Methods for Primary Objective

5.1.1.1 Hypotheses

Thirty days after the administration of MenACYW conjugate vaccine or Menomune[®] – A/C/Y/W-135, the percentages of subjects who achieve an hSBA vaccine seroresponse^a for meningococcal serogroups A, C, Y, and W in Group 1 are non-inferior to the corresponding percentages in Group 2.

Null hypothesis (H₀): $p(G_1) - p(G_2) \leq -10\%$

^a hSBA vaccine seroresponse for serogroups A, C, Y, and W is defined as:

- For a subject with a pre-vaccination titer < 1:8, the post-vaccination titer must be ≥ 1:16.
- For a subject with a pre-vaccination titer ≥ 1:8, the post-vaccination titer must be at least 4-fold greater than the pre-vaccination titer.

Alternative hypothesis (H_1): $p_{(G1)} - p_{(G2)} > -10\%$

where $p_{(G1)}$ and $p_{(G2)}$ are the percentages of subjects who achieve an hSBA seroresponse in Group 1 and Group 2, respectively. Each of the serogroups A, C, Y, and W will be tested separately.

5.1.1.2 Statistical Methods

Each of the serogroups A, C, Y, and W will be tested separately. If the lower limit of the 2-sided 95% CI of the difference between the 2 proportions is $> -10\%$, the inferiority assumption will be rejected. For the 4 non-inferiority hypotheses using the seroresponse rates, the CI of the difference in proportions ($p_1 - p_2$) will be computed using the Wilson Score method without continuity correction (7).

Let $\hat{\theta} = p_1 - p_2$, then $L = \hat{\theta} - \delta$ and $U = \hat{\theta} + \varepsilon$ are respectively the lower and the upper limits of the CI, where:

$$\delta = Z_{0.025} \sqrt{\left\{ \frac{l_1(1-l_1)}{n_1} + \frac{u_2(1-u_2)}{n_2} \right\}}$$

$$\varepsilon = Z_{0.025} \sqrt{\left\{ \frac{l_2(1-l_2)}{n_2} + \frac{u_1(1-u_1)}{n_1} \right\}}$$

l_1 and u_1 are calculated from the CI of the single proportion in Group 1 given by:

$$\frac{(2n_1p_1 + Z_{0.025}^2 \pm Z_{0.025} \sqrt{(Z_{0.025}^2 + 4n_1p_1(1-p_1))})}{2(n_1 + Z_{0.025}^2)}$$

l_2 and u_2 are calculated from the CI of the single proportion in Group 2 given by:

$$\frac{(2n_2p_2 + Z_{0.025}^2 \pm Z_{0.025} \sqrt{(Z_{0.025}^2 + 4n_2p_2(1-p_2))})}{2(n_2 + Z_{0.025}^2)}$$

where $Z_{0.025}$ is the upper 97.5th percentile of the standard normal distribution.

The overall non-inferiority of this objective will be demonstrated if all 4 individual null hypotheses are rejected.

5.1.2 Hypotheses and Statistical Methods for Secondary Objectives

5.1.2.1 Hypotheses

No hypotheses will be tested. Descriptive statistics will be presented.

5.1.2.2 Statistical Methods

Thirty days after the administration of MenACYW conjugate vaccine or Menomune[®] – A/C/Y/W-135, the hSBA geometric mean titer ratio (GMTR) between Group 1 and Group 2 will be calculated and 95% CI will be provided.

Logarithm transformation of the individual titers will be calculated. Assuming that individual $\log_{10}(\text{titer})$ is normally distributed, the 95% CI for the difference in $\log_{10}(\text{GMT})$ between Group 1 and Group 2 will be in the form:

$$\bar{X}_1 - \bar{X}_2 \pm t(1 - \alpha/2, n_1 + n_2 - 2) \cdot S \sqrt{1/n_1 + 1/n_2}$$

where $\bar{X}_i = \log_{10}(\text{GMT})$ is the mean of $\log_{10}(\text{titer})$ of Group i ,

$S^2 = [(n_1 - 1) S_1^2 + (n_2 - 1) S_2^2] / (n_1 + n_2 - 2)$ is the pooled sample variance,

n_i and S_i^2 are the sample size and sample variance of Group i ,

$t(1 - \alpha/2, n_1 + n_2 - 2)$ is the 100(1- $\alpha/2$) percentile of the t -distribution with degrees of freedom $df = n_1 + n_2 - 2$.

The 95% CI for the hSBA GMTR between Group 1 and Group 2 will be formed by taking the antilogarithms of the lower and upper limits of the 95% CI for the difference in $\log(\text{GMT})$ between both vaccine groups.

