#### *Immunogenicity*

The proportions of subjects with hSBA titers  $\geq 1:8$  obtained after MenACYW conjugate vaccine administration (Group 1) for serogroups A and C were comparable to, or for serogroups Y and W higher than, those obtained after Menomune® - A/C/Y/W-135 administration (Group 2): 93.8% in Group 1 and 85.1% in Group 2 for serogroup A; 74.9% in Group 1 and 62.8% in Group 2 for serogroup C; 80.5% in Group 1 and 59.6% in Group 2 for serogroup Y; 79.5% in Group 1 and 60.6% in Group 2 for serogroup W.

Within each group of those who received MenACYW conjugate vaccine or Menomune® - A/C/Y/W-135, the proportions of subjects with hSBA titers  $\geq 1:8$  were comparable between the subset of subjects 56 to 64 years of age and the subset  $\geq 65$  years of age, for all serogroups.

The hSBA geometric mean titers (GMTs) after MenACYW conjugate vaccine administration for serogroups A and W were comparable to, or for serogroups C and Y higher than, those after Menomune® - A/C/Y/W-135 administration. Responses with serum bactericidal assay using baby rabbit complement (rSBA) in general demonstrated the same trend as with hSBA.

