##### Visit 1 (D0): Inclusion, Randomization, Blood Sample, and Vaccination

- 1) Give the subject information about the trial, answer any questions, obtain written informed consent, and give him / her a signed copy.
- 2) Check inclusion and exclusion criteria for eligibility (see [Section 5.2.4](#) and [Section 5.2.5](#), respectively).
- 3) Collect demographic data.
- 4) Urine pregnancy test, if applicable
- 5) Obtain verbal medical history about the subject.
- 6) Conduct a history-directed physical examination, including temperature (a physical examination conducted during the same day as part of routine clinical care may be used for this purpose).
- 7) Connect to the Interactive Web Response System (IWRS) for randomization, dose number assignment, and allocation of subject number (see [Section 6.5](#) for instructions).
- 8) Obtain the first blood sample (see [Section 7.1](#) for detailed instructions regarding the handling of blood samples). If attempts to obtain the first blood draw are unsuccessful (3 attempts), then Visit 1 can be rescheduled to a later date at which point informed consent and inclusion/exclusion criteria must be re-validated. If the first blood draw cannot be obtained, the subject will be withdrawn from the study without being vaccinated.
- 9) Administer the appropriate study vaccine to the subject in the deltoid region. The vaccine must be administered on the side opposite to that of the blood sampling according to the study group:
  - Group 1 = MenACYW conjugate vaccine
  - Group 2 = Menomune® - A/C/Y/W-135
- 10) Keep the subject under observation for 30 minutes, and record any adverse event (AE) in the source document.
- 11) Give the subject a DC, a thermometer, and a ruler, and go over the instructions for their use.

- 12) Remind the subject to expect a telephone call 8 days after Visit 1 and to bring back the DC when he/she returns for Visit 2 at a specified date and time.
- 13) Remind the subject to notify the site in case of an SAE.
- 14) Complete the relevant case report form (CRF) pages for this visit.

Telephone Call 1 (8 to 10 days after Visit 1)

**Note:** If Day 08 falls on a weekend or a holiday, the telephone call may be made on the following business day. If the subject is not available, the study staff should document the attempts to make contact.

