3.2 Trial Plan

Vaccination

All subjects will receive a single dose of either MenACYW conjugate vaccine or Menomune[®] – A/C/Y/W-135 at Visit 1 (D0).

Blood sampling

All subjects will provide a pre-vaccination blood sample at Visit 1 and a post-vaccination sample at Visit 2 (30 to 44 days after the vaccination at Visit 1).

Collection of safety data

- All subjects will be observed for 30 minutes after vaccination, and any unsolicited systemic AEs occurring during that time will be recorded as immediate unsolicited systemic AEs in the electronic case report form (CRF).
- The subject will record information in a DC about solicited reactions from D0 to D07 after vaccination and unsolicited AEs from D0 to Visit 2. SAEs will be reported throughout the duration of the trial.
- The subject will record information about any possible SAEs and MAAEs in a memory aid (MA) from Visit 2 until the 6 month (+14 days) telephone call.
- In addition, the subject will be asked to notify the site immediately about any potential SAEs at any time during the trial.
- Staff will contact the subject by telephone on D08 (+2 days) to identify the occurrence of any SAE not yet reported and to remind them to complete the DC up to Visit 2 and to bring it back to Visit 2.
- The completed DC will be reviewed with the subject at Visit 2.
- Staff will contact the subject by telephone at 6 months (+14 days) after vaccination to review the MA and identify the occurrence of any MAAEs, as well as SAEs that have not been reported.

Table 3.2: Table of study procedures

Phase III Trial, 2 Visits, 1 Vaccination, 2 Blood Samples, 2 Telephone Calls,
180 Days' Duration per Subject

Visit/Contact	Visit 1	Telephone Call 1	Visit 2	Telephone Call 2
Trial timelines (days)	D0	D08	D30	D180
Time windows (days)	--	+2 days	+14 days	+14 days
Informed consent form	X			
Inclusion/exclusion criteria	X			
Collection of demographic data	X			
Urine pregnancy test (if applicable)	X			
Medical history	X			
Physical examination*	X			
Review of temporary contraindications for blood sampling†			X	
Randomization/allocation of subject number	X			
Blood sampling (BL) 10 milliliter (mL)‡	BL1		BL2	
Vaccination§	X			
Immediate surveillance (30 minutes)	X			
DC provided	X			
Telephone call		X**		X††
Recording of solicited injection site and systemic reactions	D0 to D07			
Recording of unsolicited AEs	Visit 1 through Visit 2			
DC reviewed and collected			X	
Recording of MAAEs‡‡			After Visit 2 to Telephone Call 2	

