4.4.1.4 A, C, Y, W Seroresponse

hSBA vaccine seroresponse for serogroups A, C, Y, and W is defined as:

- For a subject with a pre-vaccination titer $<$ 1:8, the post-vaccination titer must be \geq 1:16.
- For a subject with a pre-vaccination titer \geq 1:8, the post-vaccination titer must be at least 4-fold greater than the pre-vaccination titer.

rSBA vaccine seroresponse for serogroups A, C, Y, and W is defined as:

- rSBA vaccine seroresponse is defined as a post-vaccination titer \geq 1:32 for subjects with pre-vaccination rSBA titer $<$ 1:8, or a post-vaccination titer \geq 4 times the pre-vaccination titer for subjects with pre-vaccination rSBA titer \geq 1:8

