5.2.1 Full Analysis Set

The FAS is defined as the subset of subjects who received at least one dose of the study vaccine and had a valid post-vaccination serology result. All subjects will be analyzed according to the treatment group to which they were randomized.

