5.3.2 Immunogenicity

Missing data will not be imputed. No test or search for outliers will be performed.

In order to appropriately manage extreme values (undetectable responses $< \text{LLOQ}$ and $\geq \text{ULOQ}$), the following computational rule is applied to the values provided in the clinical database for each blood sample drawn for analysis purposes:

- If a value is $< \text{LLOQ}$, then use the computed value $\text{LLOQ}/2$
- If a value is between $\geq \text{LLOQ}$ and $< \text{ULOQ}$, then use the value
- If a value is $\geq \text{ULOQ}$, then use the computed value ULOQ

The derived endpoint of fold-rise is computed for extreme values, to minimize the numerator and maximizes the denominator as in [Section 4.4.1.3](#).

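### The secondary GMT ratio uses D30 titers alone; a prespecified baseline-adjusted ratio would gain modest precision from data already collected

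*SAP*

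**What the plan says.** The secondary objective compares hSBA GMTs between the two vaccines for each serogroup. Under SAP 5.1.2.2, "the hSBA geometric mean titer ratio (GMTR) between Group 1 and Group 2 will be calculated and 95% CI will be provided". The formula there is complete: the difference in mean log10 titer, plus or minus a t quantile on n1 + n2 − 2 degrees of freedom times the pooled SD times sqrt(1/n1 + 1/n2). Neither the baseline titer nor the age stratum enters. Protocol 12.1.2 promises the same ratio and interval without adjustment. On inference, SAP 5.1.2.1 says: "No hypotheses will be tested. Descriptive statistics will be presented".

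The baseline titer will exist. SAP 3.2 states: "All subjects will provide a pre-vaccination blood sample at Visit 1 and a post-vaccination sample at Visit 2". Protocol 5.1.4 (Visit 1) adds: "If the first blood draw cannot be obtained, the subject will be withdrawn from the study without being vaccinated". The primary endpoint depends on it: for subjects with a baseline of 1:8 or more, "the post-vaccination titer must be at least 4-fold greater than the pre-vaccination titer" (SAP 4.4.1.4). Fold-rise uses it too (SAP 4.4.1.3).

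No visible text in either document plans a baseline-adjusted GMT ratio. SAP 5.1.3.1.1 tabulates D0 GMTs, and SAP 5.1.4 adds GMTs by age group, gender and race. The first displays a baseline imbalance and the second gives subgroup summaries; neither adjusts the ratio.

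**The concern.** Because nothing is tested, the estimate and its 95% CI are the whole result of the secondary objective. If D30 titer correlates with D0 titer, part of the D30 variance is predictable from a value already in the database. The planned interval is then wider than it needs to be, and the ratio is not adjusted for any baseline difference that arises by chance.

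The stakes are limited. No success criterion uses the ratio, and the primary non-inferiority analysis is unaffected. A chance baseline imbalance is already allowed for in the unadjusted interval, so it is part of the same loss of precision and not a separate harm. An adjusted ratio added after unblinding would not be prespecified, so the choice belongs in the SAP now.

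**Working it through.** **Plan's own figure.** There is none to reproduce for the ratio: the visible text gives no SD, correlation, power or CI width for it, and the power sections are redacted. The one usable figure is the Protocol synopsis sample size of 450 planned and 382 evaluable per group. These agree with each other under an assumed 15% loss: 450 × 0.85 = 382.5.

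**Inputs.** n = 382 per arm (synopsis). Assumed: D30 SD of 0.7 log10; rho between D0 and D30 log10 titers from 0 to 0.6; share of baselines below the LLOQ from 0% to 80%.

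**Planned interval.** Half-width = t × SD × sqrt(2/n) = 1.963 × 0.7 × sqrt(2/382) = 0.0994 log10. Since 10^0.0994 = 1.26, the interval multiplies and divides the ratio by 1.26. Over assumed SDs of 0.4 to 0.8 this factor runs from 1.14 to 1.30.

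**Adjusted interval, no censoring.** Residual variance is SD² × (1 − rho²). Hence width ratio = sqrt(1 − rho²), and equivalent n per arm = 382/(1 − rho²).

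| rho | CI narrowing | Equivalent n per arm | CI factor at SD 0.7 |
|---|---|---|---|
| 0 | 0% | 382 | 1.26 |
| 0.2 | 2.0% | 398 | 1.25 |
| 0.4 | 8.3% | 455 | 1.23 |
| 0.5 | 13.4% | 509 | 1.22 |
| 0.6 | 20.0% | 597 | 1.20 |

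At rho 0.4 this equals 455 − 382 = 73 extra evaluable subjects per arm.

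**Cost of the extra terms.** Baseline plus two age indicators is three covariates. With N = 764, the variance of the group effect inflates by about 1 + 3/758 = 1.004, or 0.2% in width. Net narrowing is then −0.2%, 1.8%, 8.2%, 13.2% and 19.8% for the five rows.

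**Effect of the LLOQ floor.** SAP 4.4.1.1 sets values below the LLOQ to LLOQ/2, which weakens the observed correlation. A simulation (1,500 runs per setting, 382 per arm, two-fold titers, assumed baseline SD 0.5 and D30 SD 0.7, adjusting for baseline) gave this CI narrowing:

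| Latent rho | 0% below LLOQ | 40% | 60% | 80% |
|---|---|---|---|---|
| 0 | −0.1% | −0.1% | −0.1% | −0.1% |
| 0.2 | 1.9% | 1.6% | 1.3% | 0.9% |
| 0.4 | 8.0% | 6.9% | 5.8% | 4.0% |
| 0.5 | 12.9% | 11.0% | 9.2% | 6.4% |
| 0.6 | 19.3% | 16.4% | 13.6% | 9.3% |

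Coverage was 94.4% to 96.3% unadjusted and 94.3% to 96.4% adjusted, so both intervals are valid. In a separate simulation (assumed LLOQ 1:4 and D30 SD 0.65) the mean adjusted and unadjusted log10 differences agreed within 0.001, so the two methods estimate the same ratio. Narrowing there was about 1–2%, 3–4% and 8–12% at latent rho 0.2, 0.3 and 0.5. Another way of modelling the floor gives gains of the same order, somewhat smaller at 80% below the LLOQ.

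**Effect of a chance imbalance.** A baseline difference of one standard error shifts the unadjusted log10 difference by rho × 0.7 × sqrt(2/382) = rho × 0.0507. At rho 0.2 that is 0.0101, or 2.4% on the ratio; at rho 0.5 it is 0.0253, or 6.0%.

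**The case against.** The strongest reply is that nothing is broken. The planned interval is valid, the objective is descriptive, and the SAP formula delivers what Protocol 12.1.2 asks for, so this is a choice between two sound estimators. The size of the gain also cannot be established from the documents. Prior meningococcal vaccination and infection are exclusions (Protocol 5.2.5), so many baselines may sit at the floor, where the gain at rho 0.2 is only about 1%. Baseline already enters seroresponse, fold-rise and the D0 tables. Finally, the secondary endpoint is the D30 GMTs themselves, and an adjusted ratio will not exactly equal the ratio of the tabulated GMTs.

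Much of this stands. It rules out calling the plan wrong, and it means the benefit could be close to nil. It does not remove the case for adding the analysis. If rho is zero almost nothing is lost, and if rho is moderate the gain comes from data already in hand. None of the existing tables provides an adjusted ratio. The mismatch with the tabulated GMTs is real, but it is manageable because the planned ratio is still reported and the difference can be footnoted.

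The age term has thin support. Protocol 1.2.2 says that in the Phase II study MET44 the proportions with titers of at least 1:8 "were comparable between the subset of subjects 56 to 64 years of age and the subset" aged 65 and over. That concerns proportions, not GMTs, and does not separate 65–74 from 75 and older. It suggests only that age may add little precision.

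**Conclusion.** The point holds as an efficiency recommendation, not as a correction. The secondary ratio ignores a baseline titer planned for every subject. Adjusting for it would narrow the 95% CI by about 2% to 20% for assumed rho of 0.2 to 0.6 without censoring, and by about 1% to 16% if 40% to 80% of baselines are below the LLOQ. On the ratio scale at an assumed SD of 0.7, the CI factor moves from 1.26 to between 1.25 and 1.20 without censoring. The worst case is a 0.1% to 0.2% wider interval. All of this rests on assumed correlations, SDs and censoring shares, because the documents give none. No trial conclusion changes.

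**What to change.** In SAP 5.1.2.2, before unblinding, prespecify for each serogroup on the PPAS an ANCOVA of D30 log10 hSBA titer on vaccine group and log10 D0 titer, with values below the LLOQ set to LLOQ/2 as in SAP 4.4.1.1. Include age stratum (56–64, 65–74, 75 and older), since enrollment is stratified on it. Back-transform the adjusted difference and its 95% CI. Keep the planned unadjusted ratio alongside as supportive, note that the adjusted ratio need not equal the ratio of the tabulated GMTs, and report how many subjects lack a valid D0 titer.

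The cost is SAP wording and a few lines of code; no new data are needed. The downsides are small: a linearity assumption on a covariate truncated at the LLOQ, three model degrees of freedom, and the loss of subjects without a valid baseline result. That loss should fall mainly in the exploratory FAS, which requires only that a vaccinated subject "had a valid post-vaccination serology result" (SAP 5.2.1). SAP 5.3.2 gives no way to recover them: "Missing data will not be imputed".
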